UW study staff will call potential participants who opt-in to provide a detailed study overview including the benefits and potential risks of participation. If the patient is interested in participating, they will be asked questions to determine final eligibility: 1) do they have any acute medical problem requiring immediate inpatient treatment, 2) are they willing to allow their health care provider to supply lab data to the study team, or 3) are they willing to allow the study team to share high level information (graph that charts weekly scores related to the quality of your sleeping, nutrition, physical activity, memory, falls, moods, balance, pain, medication adherence and quality time spent with others, 4) do they have any plans to change health care providers in the next 18 months.

Patients who verbally confirm they want to be in the study and meet the screening criteria will be mailed the baseline survey and will receive a home visit where written consent will be obtained, the completed baseline collected, randomization determined, equipment set up, and training delivered. The baseline survey is expected to take 20-30 minutes to complete and will assess demographics, quality of life, symptom management, pain, medication adherence, and health care utilization.

Patients who consent to participate in-person at a clinic appointment will provide signed consent, be given the baseline survey, and a home visit will be scheduled to complete the activities described above.

Minority Recruitment Advisors

In addition to the general recruitment procedures described above, beginning in October 2019 three individuals active in the black community in Madison, WI will serve as advisors to the research team. They will provide feedback on recruitment materials, recruitment process, and ElderTree content and design which will inform future projects.

Patient Consent

Patients must agree to allow monitoring of their C-CHESS use and agree to allow their clinic to supply the study team with health care utilization and EHR related data, specifically lab scores for systolic and diastolic BP, weight, BMI, HDL/LDL, HbA1C, and pain. (as applicable to the patient), and diagnoses of anxiety, depression, osteoporosis, and cancer. The patient will be given the right not to share specific information and will retain the right to revoke their permission at any point.

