Participants who do not already own a computer will be receiving a laptop as part of the study. The laptop has an administration interface that allows our technical team to access devices remotely if a participant calls tech support or reports a problem. If a participant loses their laptop or installs something that is causing problems, we have the ability to remotely wipe the device, lock it down, restore the operating system and/or run a security check. We can also do security updates remotely to make sure patches are up to date on each laptop and security software has not been disabled by the user.

Patient Randomization: Once informed consent and baseline measures have been obtained from patients, they will be randomized to either the experimental (TAU + C-CHESS) or control (TAU + Internet) group, stratified on gender, clinic site, and number of chronic conditions (3-5 vs. 6+). Patients who are in the experimental group will be further randomized into two groups, one will be asked to identify a health outcome to track and share with their physician using the Clinician Report and the other group will not.

When baseline assessment and consent are complete, the researcher will enter the participant number and randomization data into a randomization spreadsheet. The interviewing researcher, once informed of group assignment, will provide setup and training.

The research staff will train participants to use C-CHESS and customize it (e.g. by health condition) during a home visit. Participants will be asked to check in regularly, initially at a daily rate with frequency of at least weekly over the course of the study.

Patient Qualitative: Data will be gathered via an interview at 3 times from 6 patients at each of the 5 clinics (N=30). Each interview is expected to take 30-60 minutes and will take place either in-person at a place of the subjects choosing or via phone.

Recruitment: Participants will be identified through a consent form opt-in question and demographics as reported on the baseline survey. We will seek a mix of genders and number of chronic conditions. We will also look at C-CHESS use data to find a mix of users and non-users. We will contact potential participants by messaging them through the C-CHESS application or phoning them.

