This analysis plan should allow us to examine treatment-related change with regard to: 1) condition-specific clinical outcomes; 2) general outcomes reflecting disease coping and burden; and 3) condition-specific clinical outcomes when modeled as a composite score that reflects status with regard to the 5 major conditions.

Effectiveness of TAU+Internet vs. TAU+C-CHESS. We will use separate mixed-effects models to evaluate the primary and secondary outcomes. Each model will include fixed effects for TAU+Internet vs. TAU+C-CHESS, time (6, 12, and 18 months), and the arm-by-time interaction, including the baseline assessment of each outcome as a covariate. We will also determine whether clinic exerts main effects or interacts with the treatment condition. The latter will test the consistency of C-CHESS effects over different clinics and whether data can be pooled across sites. The initial intercepts will be modeled as random variables to estimate variance and covariance of intervention effects at the different fixed occasions, and across and between patients. These models account for dependence among successive observations made on the same patient and use all available data (not just complete cases). We will conduct treatment time contrasts between and within groups to test time-based effects, with our primary analysis focused on the C-CHESS effect at 12 months. Generalized linear mixed-effects models will be used for the count outcomes addressing primary care use. If a count outcome has sufficient variability, Poisson regression will be used; if not, the outcome will be coded as dichotomous (some service use vs. none) and logistic regression will be used.

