Impact on power calculations of adding attention control and the Clinician Report. We are using a placebo comparison group to remove the Hawthorne effect, not to contribute to managing chronic conditions. Conversely, the addition of the Clinician Report to the Elder Tree system upon which C-CHESS is based should have a positive effect. We compared CHESS to CHESS+CR in a lung cancer RCT and found statistically and practically significant improvement in symptom distress by adding the CR. Overall, we believe this change will make our power analyses conservative.

Missingness

In previous work, we completed 85% of interviews at 4, 8, and 12 months and kept missing data on core interview items to about 2%; we expect these rates in this study. In primary care, data are not likely to be missing at random (i.e., the probability that data are missing relates to what the data would have been had the data been observed). Because this may lead to biased parameter estimates for our models, we will identify missing data patterns and use pattern-mixture modeling to test the sensitivity of our longitudinal intervention analysis to missing data assumptions,^{107,108} and conduct other sensitivity analyses after imputing missing data with a range of clinically plausible values based on explicit assumptions for the missing data (e.g., best-case, worst-case; with and without multiple imputation).^{109,110}

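### With baseline as a covariate, the main models exclude any patient who has follow-up values but no baseline; this mainly affects the EHR-sourced secondary outcomes and costs precision

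*Combined protocol and SAP*

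**What the plan says.** Section 6.0 (Effectiveness of TAU+Internet vs. TAU+C-CHESS) specifies separate mixed-effects models for the primary and secondary outcomes. The fixed effects are arm, "time (6, 12, and 18 months), and the arm-by-time interaction", "including the baseline assessment of each outcome as a covariate". Baseline is therefore a predictor, not one of the response rows. The same paragraph says that the models "use all available data (not just complete cases"), "with our primary analysis focused on the C-CHESS effect at 12 months".

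The baseline values have two sources:

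- **Survey.** Section 3.0 (Patient Recruitment) says that the baseline survey "will assess demographics, quality of life, symptom management, pain, medication adherence, and health care utilization". It contains no blood pressure, LDL or HbA1c. Section 3.0 (Patient Randomization) adds: "Once informed consent and baseline measures have been obtained from patients, they will be randomized".
- **Clinic records.** Section 3.0 (Patient Consent) has the clinic supply blood pressure, weight, BMI, "HDL/LDL, HbA1C, and pain. (as applicable to the patient"), extracted quarterly from the EHR. Patients may decline to share specific items. No baseline window and no study-ordered baseline test are given.

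Section 8.0 (Missingness) reports that earlier work "kept missing data on core interview items to about 2" per cent. It plans pattern-mixture models and imputation as sensitivity analyses. It does not mention baseline covariates.

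**The concern.** A likelihood-based mixed model handles an absent follow-up visit by using the visits that were observed. It cannot do the same for an absent covariate. Unless the value is imputed or baseline is made a response, every follow-up row of that patient is lost, even when all three visits are present.

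For the EHR outcomes a patient can be validly randomised without a usable baseline value, because the measures required before randomisation appear to be those in the survey. Condition-specific analyses already use only patients with the diagnosis, so they have the least information to spare. At stake are the precision of those secondary tests and of the composite, and how far the analysed group represents the randomised patients with the condition. If no rule is written, software defaults or a decision made after seeing the data will supply one.

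**Working it through.** **Inputs from the documents.** d = .40, two-sided alpha .05, power .80, 100 per arm, then 132 per arm after the step for condition clusters, and 20% attrition to 330 (section 8.0). About 2% item missingness, for interviews only (section 8.0).

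**Assumptions.** Share p of diagnosed patients without a baseline: 10%, 20%, 30%. Correlation r between baseline and follow-up: .6, with a range of .5 to .7. The documents give neither.

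**1. The plan's own figure.** The normal formula gives 99 per arm for d = .40 at power .80, and the t-based solution is 99.1, so 100 per arm is reproduced. 264 / (1 − .20) = 330 is also reproduced. The documents give no formula for the step from 100 to 132 per arm.

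**2. The mechanism.** The planned model was fitted to one simulated data set of 264 patients with 3 × 264 = 792 follow-up rows, 53 patients lacking a baseline. It kept 211 patients and 633 rows. All 3 × 53 = 159 follow-up rows of the 53 patients were lost.

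**3. Loss of precision, single follow-up.**

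- Deletion keeps a fraction 1 − p of the information, so the standard error is multiplied by 1/√(1 − p).
- With baseline as a response, a patient without a baseline still contributes, with residual variance 1 rather than 1 − r². The information kept is (1 − p) + p(1 − r²) = 1 − p·r².

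| p | SE factor, deletion | Information kept, baseline as response (r = .6) | SE factor |
|---|---|---|---|
| 10% | 1/√.90 = 1.054 | 1 − .10 × .36 = .964 | 1.019 |
| 20% | 1/√.80 = 1.118 | 1 − .20 × .36 = .928 | 1.038 |
| 30% | 1/√.70 = 1.195 | 1 − .30 × .36 = .892 | 1.059 |

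For r from .5 to .7, the last column runs 1.013–1.025, 1.026–1.053 and 1.040–1.083.

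**4. Cross-check with all three follow-ups.** This is a generalised least squares calculation with compound symmetry, r = .6 and 132 per arm. The SE of the 12-month arm effect is 0.0985 with no baseline missing.

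| p | Deletion | Baseline as response |
|---|---|---|
| 10% | 0.1038 | 0.0999 |
| 20% | 0.1101 | 0.1016 |
| 30% | 0.1177 | 0.1033 |

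The ratios to 0.0985 are 1.05, 1.12 and 1.19 for deletion, and 1.01, 1.03 and 1.05 for baseline as a response. The single-follow-up table slightly understates the gain.

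**5. Quality of life.** At p = 2%, 1/√.98 = 1.010, which is about 1% of the standard error.

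**6. Power depends on the scale of d.**

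- Unadjusted at 99 per arm, power of .80 falls to .76, .71 and .65 with deletion at p = 10%, 20% and 30%.
- If d = .40 is on the raw SD scale, adjustment at r = .6 makes the effective d equal to .40/√(1 − .36) = .50. Power is then .94 with none missing, .91, .88 and .83 with deletion, and .93, .92 and .91 with baseline as a response. At r = .5 and 30% missing, deletion gives .77.
- Unadjusted at the plan's 132 per arm, power is .90 with none missing and .87, .83 and .78 with deletion.

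**The case against.** Several points on the other side stand.

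- **The sentence about all available data.** A reader might infer that it is simply false. It follows a clause on successive observations within a patient and contrasts the models with complete-case analysis of repeated measures. For incomplete follow-up it is correct. Nor does the plan say that patients without a baseline are dropped; exclusion is the consequence of the specified model when no rule is given.
- **How common the problem is.** Section 2.0 requires at least 18 months of prior treatment in the clinic and willingness to share these values, and the affected patients carry the diagnosis. An earlier value is likely, especially for blood pressure. The phrase "HDL/LDL, HbA1C, and pain. (as applicable to the patient") most naturally means tests relevant to the patient's conditions and is not evidence of missing values. Without a window, however, nobody can say which earlier value counts.
- **The primary outcomes.** Quality of life is surveyed before randomisation. Primary care visits over the previous 18 months are extracted at screening. Neither is materially exposed, and pain is also in the baseline survey.
- **Bias and intention to treat.** A reader might infer that the arm comparison is biased. Baseline precedes randomisation and the exclusion rule is the same in both arms, so it need not bias the comparison.
- **Power.** A reader might infer that power falls to .76, .71 or .65. Those figures take patients lost only in an adjusted model away from an unadjusted calculation at 99 per arm. The documents do not say that d = .40 is already baseline-adjusted, so the figures cannot be presented as the plan's power.
- **Imputation.** Section 8.0 does not limit multiple imputation to outcomes, so it could fill covariates. It is offered only as a sensitivity analysis, which leaves the main analysis as described.

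**Conclusion.** The point holds in a limited form. In the main models, use of all available data is assured only for patients with a baseline value; those with follow-up values and no baseline are excluded. The exposure lies mainly in blood pressure, LDL, HbA1c and the composite. The inflation of standard errors under deletion depends only on the assumed missing share; the advantage of baseline as a response also depends on r. The documents settle neither quantity, and the true missing share may be below the range shown. The demonstrated cost is lost precision and a narrower analysed population. The documents support neither a bias in the arm comparison nor a specific power figure. The change is still worth making, because a better method is available at almost no cost.

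**What to change.** 1. **Continuous outcomes.** Model baseline as the first of four repeated measures (0, 6, 12 and 18 months), constrain the two arms to a common baseline mean, and keep the 12-month arm contrast. Every randomised patient in the relevant analysis set with any follow-up value then contributes.
2. **EHR baseline window.** Before unblinding, define which record values count as baseline for blood pressure, LDL and HbA1c, and which value is taken when there are several.
3. **Count and logistic models.** Fill a missing baseline with an arm-blind value plus a missing indicator, or use multiple imputation. Describe the result as approximately, not exactly, unbiased for the logistic models, where the odds ratio is non-collapsible.
4. **Reporting.** Give the number of patients without a baseline, by arm and outcome.

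The cost is SAP wording and standard mixed-model code, with no new data. With complete baselines the result is essentially the same as from the planned model.

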1.0 STUDY OBJECTIVES

This project will test the use of an eHealth intervention called C-CHESS, to modify health behaviors and improve health outcomes in older adults with comorbid chronic diseases and health conditions.

Aim 1 Refine C-CHESS, using feedback from patients and primary care clinicians.

Aim 2 Conduct a randomized clinical trial to test 4 hypotheses:

1. *Primary outcomes:* Patients assigned to TAU+C-CHESS will have better quality of life and less primary care use (fewer visits) than those assigned to TAU+Internet.
2. *Secondary outcomes:* Patients assigned to TAU+C-CHESS will have improved composite scores; improved individual condition outcomes (mm Hg for hypertension, mg/dL for hyperlipidemia (LDL), HbA1c for diabetes, and pain for arthritis); and fewer symptoms from a list than patients assigned to TAU+Internet.
3. *Mediators:* Patients assigned to TAU+C-CHESS will have, compared with patients assigned to TAU+Internet, greater adherence to medications and appointments as well as improved competence,

relatedness, and autonomy.

4. *Moderators:* Improvements in primary outcomes for TAU+C-CHESS vs. TAU+Internet will be greater for women than men, those ≥ 75 vs. 65 to 74, and those with 3-5 chronic conditions vs. 6+.

Aim 3 Analyze data from the RCT and publish results.

Exploratory questions:

- Does C-CHESS reach a large proportion of targeted patients, get a large proportion of targeted clinicians to use C-CHESS, get a large proportion of patients to regularly use C-CHESS, and maintain that performance over time)?
- Does the use of specific C-CHESS services affect outcomes?
- Does the use of C-CHESS affect other health service use?

Primary Aim

Patients assigned to TAU+C-CHESS will have better quality of life and fewer primary care visits than those assigned to TAU+Internet.

C-CHESS will contain the Clinician Report to make it easier for PCPs to respond to important patient changes, pilot data suggested that primary care visits could be reduced. Reducing the number of primary care visits will both lessen provider burden and ultimately reduce healthcare costs.

Secondary Aim

Patients assigned to TAU+C-CHESS will have improved composite scores; improved individual condition outcomes (mm Hg for hypertension, mg/dL for hyperlipidemia (LDL), HbA1c for diabetes, and pain for arthritis); and fewer symptoms from a list than patients assigned to TAU+Internet.

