8.0 STATISTICAL CONSIDERATIONS

Power analyses for primary and secondary outcomes. Our power analysis was based on Elder Tree pilot data and other studies that examined the impact of behavioral interventions on single chronic conditions.⁹⁵ A meta-analysis⁹⁶ of self-management interventions found significant effects on HbA1c for diabetics ($d = .36$), and on systolic blood pressure among hypertensives ($d = -.39$). Other studies found a moderate effect size ($d = .61$) on pain behavior⁹⁷ and a small effect on number of primary care visits ($d = .28$) when patients attended self-management and peer-support meetings.^{98,99}

Because effect sizes vary for interventions of chronic conditions, we want our expected effect sizes to be conservative and yet clinically meaningful. We therefore chose an effect size of $d = .40$ for our primary

outcomes (quality of life and primary care use) as well as individual condition measures (secondary outcomes) and the composite score based on them. Adequate power ($1-\beta = .80$, two-tailed $\alpha = .05$) would require a final sample of $N=200$ patients (100 per arm).¹⁰⁰ Since we will examine 4 clusters, with 3 conditions per cluster, we will need 132 per arm. Assuming 20% attrition, we will recruit $N=330$ patients (33 per arm per clinic). This should also be sufficient for detecting similar effect sizes (at a power of $1-\beta = .80$) for condition-specific changes in diabetes,¹⁰¹ hypertension,¹⁰² and arthritis.¹⁰³ The literature is less clear in hyperlipidemia but 50% of patients are non-adherent to statins,¹⁰⁴ and statins have a high effect size,¹⁰⁵ so our goal may be achievable.

Power for mediation and moderation analyses. Power for detecting parameter changes in the structural model was estimated using a procedure of Satorra and Saris¹⁰⁶ that approximates the non-central chi-square distribution. A total N of 220 patients will provide adequate power ($> .80$) to detect a group difference in a parameter by moderate .4 standard deviations. With an N of 264 in our primary analysis, we are confident our secondary analysis will have adequate power.

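### Primary care visits are committed to a Poisson mixed model with random intercepts only; if visits are overdispersed within a period, the 12-month test is anti-conservative, and a negative binomial model would guard against this at little cost.

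*Combined protocol and SAP*

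**What the plan says.** Section 1.0 makes visits co-primary with quality of life: patients given C-CHESS "will have better quality of life and less primary care use (fewer visits) than those assigned to TAU+Internet".

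The analysis is in section 6.0, under the paragraph on effectiveness of the two arms:

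- Model class: "Generalized linear mixed-effects models will be used for the count outcomes addressing primary care use".
- Distribution: "If a count outcome has sufficient variability, Poisson regression will be used". Otherwise the count is reduced to any use against none and analysed by logistic regression.
- Random terms: "The initial intercepts will be modeled as random variables". The rest of that sentence gives the purpose as estimating variances and covariances of intervention effects across the fixed occasions and across patients.
- What the models are meant to handle: "These models account for dependence among successive observations made on the same patient".
- Fixed effects: arm, "time (6, 12, and 18 months), and the arm-by-time interaction, including the baseline assessment of each outcome as a covariate".
- Primary contrast: "with our primary analysis focused on the C-CHESS effect at 12 months".

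Section 8.0 sets a two-sided alpha of .05. Its planned sensitivity analyses concern missing data only. Neither section mentions a dispersion parameter, a negative binomial or quasi-Poisson model, an observation-level random effect, a robust standard error or a check for overdispersion.

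**The concern.** Given a patient's intercept, a Poisson model forces the variance of that patient's count in a period to equal its mean. The intercept captures stable differences between patients. It does not capture a cluster of visits in one period, such as those around an acute illness or after a hospital discharge. The primary contrast rests on one occasion, so unmodelled variation at that occasion enters its error directly.

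The plan's one distributional safeguard covers counts that vary too little. It has no provision for counts that vary too much, which is the case in which Poisson standard errors are too small. At stake are the type I error and the interval width for one of the two primary outcomes.

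**Working it through.** **The plan's own figures.** For d = .40, 80% power and two-sided .05, n per arm = 2(1.960 + 0.842)²/0.40² = 98.1, so 99, against the stated 100 (power at 100 per arm: .807). With 132 per arm, 264 are analysed, and 264/0.80 = 330 recruited. These figures reproduce. They rest on a standardised mean difference and contain no Poisson assumption, so this point leaves them untouched.

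**Inputs from the documents.** 132 per arm; occasions at 6, 12 and 18 months; baseline value as covariate; random intercept; Poisson; arm contrast at 12 months; two-sided .05.

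**Assumed inputs (the documents give no visit distribution).** Visits are counted over the six months ending at each occasion. Mean 1.5 to 4 visits per period. Patient intercept SD 0.3 to 0.8 on the log scale. Within-period gamma variation φ from 0 to 1, so that for a patient with mean μ

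Var(Y | patient) = μ + φμ².

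At μ = 2.5 this is 2.5 for φ = 0, 3.125 for 0.1, 4.06 for 0.25, 5.63 for 0.5 and 8.75 for 1.0. That is 1, 1.25, 1.63, 2.25 and 3.5 times the Poisson variance.

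**Simulation under no arm effect.** The planned model was fitted by maximum likelihood with Gauss–Hermite quadrature and a Wald test at 12 months. There were 264 complete cases, no clinic effect and 2,000 replicates per setting (Monte Carlo SE = √(.05 × .95/2000) = .005).

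| Mean visits | Patient SD | φ | Model SE / true SE | Type I error |
|---|---|---|---|---|
| 2.5 | 0.5 | 0 | 1.01 | 5.0% |
| 2.5 | 0.5 | 0.1 | 0.96 | 6.1% |
| 2.5 | 0.5 | 0.25 | 0.88 | 8.2% |
| 2.5 | 0.5 | 0.5 | 0.81 | 11.0% |
| 2.5 | 0.5 | 1.0 | 0.69 | 17.1% |
| 1.5 | 0.5 | 0.25 | 0.91 | 7.0% |
| 1.5 | 0.5 | 0.5 | 0.86 | 9.2% |
| 4 | 0.5 | 0.25 | 0.82 | 10.5% |
| 4 | 0.5 | 0.5 | 0.75 | 13.7% |
| 2.5 | 0.3 | 0.5 | 0.81 | 10.9% |
| 2.5 | 0.8 | 0.5 | 0.71 | 17.0% |

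Hand check at mean 2.5, SD 0.5, φ = 0.5: the mean model SE is .1104 and the empirical SD is .1360, a ratio of .812. The expected rejection rate is 2Φ(−1.96 × .812) = 2Φ(−1.59) = .11, as simulated.

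A separate simulation (1,000 replicates per setting, patient SD 0.5, means 2 and 3) agrees. It gave .041 at φ = 0 (mean 2), .063 (mean 2) and .102 (mean 3) at 0.25, .116 and .131 at 0.5, and .166 at 1.0 (mean 2).

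**How much the intercept absorbs.** At mean 2.5 and patient SD 0.5, its estimated SD rises from 0.40 to 0.75 as φ goes from 0 to 1. It takes up part of the extra variation, but not enough to protect the 12-month test.

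**Remedies.** At mean 2.5, SD 0.5, φ = 0.5 (600 replicates), Poisson gave 11.3%, a negative binomial mixed model 5.2%, and patient-clustered sandwich errors on the Poisson fit 5.2%. Over the 2,000-replicate settings the sandwich version gave 4.7–5.3%, except 6.5% at φ = 1.0 and 7.7% at patient SD 0.8. In the separate simulation it ranged from .038 to .067.

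**The case against.** A reader might infer that the planned test fails its alpha. The documents do not support that. They give no visit mean, variance or correlation between periods, and the test holds its level at φ = 0 and nearly so at 0.1. Section 2.0 requires at least 18 months of prior treatment at the clinic, so follow-up could be scheduled and regular. With visits more evenly spaced than Poisson (Erlang-2 gaps, 600 runs), type I error was .020 at mean 2 and .022 at mean 3, which is conservative. On the other side, the background says that health can worsen quickly in these patients, and the eligible conditions include COPD and heart failure. Bunching is therefore plausible but not established. The higher rates also imply weak stability between periods: a baseline-to-12-month correlation of about .13 (φ = 1.0, mean 2) or .23 (φ = 0.5, mean 3), against .36 with no bunching.

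A reader might also take the tabulated rates as the chance of falsely declaring that C-CHESS reduces visits. They are two-sided. False rejections favouring C-CHESS were .037 (φ = 0.25, mean 2), .072 (0.5, mean 3) and .082 (1.0, mean 2), against a nominal .025.

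Finally, the part of the random-effects sentence about fixed occasions could mean occasion-level random effects, which would absorb the bunching. The text names only intercepts, so that reading cannot be relied on. If it was intended, the plan should say so.

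What stands is that the plan makes no provision for overdispersion in a primary outcome, and that the usual remedy is simple.

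**Conclusion.** The point holds conditionally. As written, the visit analysis has no protection against extra-Poisson variation within a period. If such variation exists, the 12-month standard error is too small and the two-sided .05 test is anti-conservative. Under the assumed means and patient SDs, type I error is about 5% at φ = 0, 6% at 0.1, 6–10% at 0.25, 9–17% at 0.5 and 17% at 1.0, with about half of false rejections in favour of C-CHESS. The size rests on assumed dispersion, complete data and no clinic effect. Quality of life is not affected. This is a should-fix: a cheap improvement to a primary analysis, not a demonstrated loss of alpha control.

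**What to change.** In section 6.0, replace Poisson regression with a negative binomial mixed model for the visit counts (random patient intercept plus a dispersion parameter), and keep the 12-month rate ratio as the reported effect. If dispersion is absent, this essentially reduces to the planned model. Name the Poisson model with patient-clustered robust standard errors as a fallback or sensitivity analysis only, because it was slightly liberal in the harsher settings. State in the same place whether any random effect beyond the patient intercept is intended. Make the change before outcomes are seen by arm, since a count model chosen afterwards is open to challenge.

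The cost is one sentence and no new data. The interval widens only if overdispersion is present. At mean 2.5 and φ = 0.5, an honest interval would be about 1/.812 = 1.23 times as wide on the log scale. The negative binomial model was tested at one setting only, so a short check over the sponsor's expected visit rates would be sensible.
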